3.3.1 General Guidance for Dose Modifications

- 3.3.1.1 Patients may continue to receive therapy provided the following criteria are met on Day 1 of each cycle:
 - Non-hematologic toxicity recovered to < Grade 2 (or tolerable Grade 2 or baseline).
 - No evidence of progressive disease.
- 3.3.1.2 In the event of an adverse event at least possibly related to the investigational agent, the dose of the investigational agent should be adjusted according to the parameters articulated above and guidelines listed in the Dose Delays / Dose Modifications tables shown below (**Table 9** and **Table 10**). If an adverse event is not covered in such tables, doses may be held at the discretion of the investigator for the subject's safety.

3.3.1.3 If patients fail to recover to CTCAE Grade 0-1, tolerable Grade 2 (or within 1 grade of starting values for pre-existing laboratory abnormalities), or baseline from a treatment-related adverse event attributable to DAC-THU within 42 days (2 cycles), they cannot receive additional DAC-THU. Patients may continue pembrolizumab monotherapy at the investigator discretion provided that discontinuation criteria for pembrolizumab toxicity have not been met.

3.3.2 Treatment Delays and Modifications for Medical Needs

Brief interruptions and delays up to 3 weeks may be required due to patients experiencing complications of their disease or other medical illness not attributable to disease progression, or protocol therapy. A patient that interrupts therapy for more than 3 weeks will be taken off treatment.

3.3.3 Dose Reductions

No dose reductions of Pembrolizumab are permitted on this study.

3.3.4 Dosage Modification and Management of Immune-Related Adverse Events

Since inhibition of PD-L1 stimulates the immune system, irAEs may occur. Treatment of irAEs is mainly dependent upon severity (NCI-CTCAE grade):

- Grade 1 to 2: treat symptomatically or with moderate dose steroids, more frequent monitoring.
- Grade 1 to 2 (persistent): manage similar to high grade AE (Grade 3 to 4).
- Grade 3 to 4: treat with high dose corticosteroids.

Treatment of irAEs should follow accepted guidelines set forth in Table 10.

3.3.5 Dose Modification of DAC-THU

Table 9 lists standard laboratory values that should trigger dose modifications of the investigational drug.

General Adverse Events	Action		
Non-hematological, Grade 1 or 2 (excluding hemorrhage)	 Continue DAC-THU therapy at full dose prescribed. Apply maximum supportive care recommendations. If prolonged duration of Grade 2 adverse event (≥ 7 days) is affecting quality of life, start the next treatment cycle at DL-1. If event persists and continues to affect quality of life for ≥ 7 more days following initial dose reduction, discontinue DAC-THU. 		
Grade 3 ALT and AST	 Hold DAC-THU therapy until recovery to Grade ≤ 1. If ALT and AST resolve to Grade ≤ 1 within 10 days, maintain current dose level. If ALT and AST do NOT resolve to Grade ≤ 1 within 10 days, dose reduce 1 level. If Grade 3 ALT or AST occurs after dose reduction, discontinue DAC-THU. 		

 Table 9: Trigger Values that Result in Dose Modification

General Adverse Events	Action	
Grade 4 ALT and AST	 Hold DAC-THU therapy until recovery to Grade ≤ 1. Resume DAC-THU at DL-1. If Grade 4 toxicities occur after dose reduction, discontinue DAC-THU. 	
Non-hematological, Grade 3 or 4 (excluding ALT, AST, hemorrhage and QT prolongation)	 Apply maximum supportive care recommendations. Hold DAC-THU until recovery to Grade ≤ 1 and resume DAC-THU at the next lower dose level. If symptoms continue to persist at Grade 3 or 4, following dose reduction, discontinue drug. 	
QT prolongation, Grade 3 or 4	 Cardiology consultation will be obtained to determine whether any cardiac functional assessment is warranted or if therapy should be delayed or discontinued. When warranted, ECGs will subsequently be reviewed by the NCI consulting cardiologist. If therapy is continued, dose reduce 1 level for Grade 4 events. If Grade 3 or 4 toxicities occur after dose reduction discontinue DAC-THU. 	
Thrombocytosis	 If platelet count > 500/ mcL but < 1.2M/mcL, continue DAC-THU at current dose. Begin ASA 325mg PO daily. If platelet count 1.2M /mcL or more, hold DAC-THU until platelet count < 1.2 M/mcL, begin ASA 325 mg PO daily and resume DAC-THU at DL-1 if within the first two Cycles of Course 1; or at SAME dose or DL-1 per PI discretion in subsequent cycles. 	
Hemoglobin	• Hgb > 18 g/dL: hold DAC-THU until Hgb WNL. Resume DAC-THU at DL-1.	
Hematological Adverse Events		
Grades 1 and 2 events	• Continue DAC-THU therapy at full dose prescribed. Apply maximum supportive care recommendations.	
Grade 3 events	 Apply supportive care. Apply supportive care. If toxicities occur in the first two cycles of therapy and resolve to Grade 1 or less, in 10 days, resume DAC-THU at current dose. If toxicities occur in the first two cycles of therapy and resolve to Grade 1 or less > 10 days following drug hold, resume DAC-THU at next lower dose. If toxicities occur in subsequent cycles and resolve to Grade 1 or less in 21 days following drug hold, resume DAC-THU at SAME dose. If toxicities recur within two cycles of resuming DAC-THU, hold until toxicities resolve to Grade 1 or less, and resume DAC-THU at next lower dose. If toxicities occur in subsequent cycles and resolve to Grade 1 or less, and resume DAC-THU at next lower dose. 	

General Adverse Events	Action		
Grade 4 events	 Grade 1 or less > 21 days following drug hold, resume DAC-THU at next lower dose. If toxicities recur within two cycles after maximal dose reduction, discontinue DAC-THU. Apply maximum supportive care recommendations. Hold DAC-THU therapy until patient meets hematologic criteria for retreatment and resume DAC-THU at next lower dose. 		
	• If recurrence of hematological adverse event after drug hold/ interruptions is observed with treatment at DL-1, in the setting of maximum supportive care measures applied, hold drug once again until patient meets hematologic criteria for retreatment, further dose reduce DAC-THU if possible or discontinue DAC-THU per PI discretion.		

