Adverse events: Non-cytotoxic modification of hematopoietic differentiation by DAC is expected to simultaneously increase platelet counts and decrease absolute neutrophil counts (shown *in vitro* and in clinical studies with DAC alone ($\underline{60}$, $\underline{61}$, $\underline{74}$, $\underline{75}$)). This expected pattern in blood counts was seen in subjects receiving oral DAC 0.08 and 0.16 mg/kg (dose levels 4 and 5) with the steepest

blood count changes observed at the highest dose (**Figure 14**). Platelet and neutrophil counts on therapy did not reach the *a priori* defined triggers for dose modification, that is, neither a platelet count of > 1200 x 10⁹/L, nor an absolute neutrophil count < $1.5 \times 10^{9}/L$, were reached (the highest platelet count on therapy was $1122 \times 10^{9}/L$ in a subject with a pre-treatment count of 733 x 10⁹/L, and the lowest absolute neutrophil count on therapy was $1.6 \times 10^{9}/L$ in a subject with a pre-treatment count of $1.8 \times 10^{9}/L$) (**Figure 14**). Of particular relevance to this protocol, absolute lymphocyte counts remained stable during and subsequent to the eight-week THU-DAC therapy (**Figure 15**). The pattern of adverse events was similar between subjects receiving placebo or oral THU-DAC in all dose cohorts (**Table 3A**). There were no significant adverse events, including no significant gastro-intestinal adverse events, attributed to study drug (**Table 3B**). The most frequent adverse event in placebo and study drug treated subjects was pain from vaso-occlusive sickle cell crisis (**Table 3A**). There were no Grade 4 adverse events in placebo or study drug treated subjects (**Table 3**). No subjects discontinued placebo or study drug because of adverse events.

[figure not shown]

Figure 14: Platelet counts increased and absolute neutrophil counts simultaneously decreased during repeat dose administration, the blood count profile expected from non-cytotoxic DNMT1 depletion. A) Study schema showing repeat dose administration 2X/week for 8 weeks. B) Platelet counts. C) Absolute neutrophil counts (ANC).

[figure not shown]

Figure 15: Absolute lymphocyte counts in SCD patients treated with increasing doses of THU-DAC.

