Efficacy/Pharmacodynamic Effects: Hemoglobin F levels were measured by HPLC through the Clinical Pathology laboratory and also by flow cytometric quantification of HbF in individual red cells. Significant increases in HbF were observed by both these measurements at dose levels 4 and 5 (DAC 0.08 and 0.16 mg/kg respectively), with the greatest increases occurring at dose level 5 (**Figure 16**). These HbF increases were associated with trends for increasing total hemoglobin, decreasing LDH and total bilirubin (as biomarkers of hemolysis) and decreasing D-dimer levels (as a biomarker of coagulation pathway activation and vaso-occlusion) (**Figure 17**). Increases in HbF were not sustained once study drug was stopped in Week 8 (**Figure 16**).

Hematologic side-effects and toxicity: There were no hematologic toxicities warranting treatment hold (please see above).

Non-hematologic toxicity: No significant non-hematologic toxicities were observed (please see above).

In summary, results from the aforementioned Phase 1 clinical trial of oral THU-DC demonstrate that the non-human primate data essentially mapped to subjects with high risk SCD: combining a

mini-dosage of oral DAC (0.16 mg/kg; ~5 mg/m²) with THU 10 mg/kg produced major improvement in DAC tissue distribution and exposure, creating a wide DAC concentration-time profile that is desired for DNMT1-depletion without cytotoxicity in vivo. This DAC oral dosage compared very favorably to parenteral dosages FDA approved for administration to humans (20-45 mg/m²/day for 3-5 days every 4-6 weeks). The THU-DAC was very well-tolerated without significant gastro-intestinal or other drug-related adverse events with repeat administration 2X/week for 8 weeks. Changes in hematologic parameters were those expected from non-cytotoxic DNMT1-depletion by DAC, with simultaneous increases in platelet counts and hemoglobin and decreases in absolute neutrophil counts. The platelet and absolute neutrophil count changes did not cross thresholds that would have triggered treatment holds (> 1,200 x 10⁹/L for platelets, < 1.5 x 10⁹/L for neutrophils). Increases in HbF that would be considered clinically significant if generated by standard of care HU therapy were observed at DAC dosage of 0.08 and 0.16 mg/kg. The HbF increases were associated with favorable trends in total hemoglobin and in peripheral blood markers of hemolysis and coagulopathy/vaso-occlusion – serum LDH, total bilirubin and D-dimer.

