- 2.1.2.12 History or current evidence of any condition, therapy, or laboratory abnormality that might confound the results of the trial, interfere with the subject's participation for the full duration of the trial, or is not in the best interest of the subject to participate, in the opinion of the treating investigator.
- 2.1.2.13 Psychiatric or substance abuse disorders that would interfere with cooperation with the requirements of the trial.
- 2.1.2.14 Thrombocytosis defined as platelet count > 1,200,000/mcL.

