4 CONCOMITANT MEDICATIONS/MEASURES

4.1 HEMATOLOGIC AND BLOOD PRODUCT SUPPORT

Blood product support should be provided to maintain platelets > 20,000 cells/mcl, Hgb > 8.0 gm/dl and as clinically indicated. Growth factor support is not permitted with exception of administration of filgrastim. Filgrastim will not be administered prophylactically, but may be administered if a patient experiences neutropenic sepsis, or if clinically indicated.

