8.1.1 Adverse Event

Any untoward medical occurrence in a patient or clinical investigation subject administered a pharmaceutical product and which does not necessarily have a causal relationship with this treatment. An adverse event (AE) can therefore be any unfavorable and unintended sign (including an abnormal laboratory finding), symptom, or disease temporally associated with the use of a medicinal (investigational) product, whether or not related to the medicinal (investigational) product (ICH E6 (R2)).

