1. Thrombocytosis: Decitabine-induced shifts in differentiation include increased erythropoiesis and megakaryopoiesis (60, 61). Therefore, increases in platelet counts are expected, especially in patients who are hyposplenic (e.g., patients with SCD) or asplenic (many patients with β -thalassemia). Although it is intuitive to expect an association between platelet count and thrombosis risk, this has not been evident in clinical observations and studies, whereas qualitative RBC defects from underlying disease can be pro-thrombotic (60, 117-124). Hence, in a SCD study, SC decitabine-induced improvement in multiple indices of RBC pathology was accompanied by improvement in multiple markers of coagulation pathway activity, despite concurrent platelet count increases to > 800x10⁹/L (60). Thus, it is possible that decitabine-induced improvements in RBC phenotype could reduce thrombophilia despite concurrent platelet count increases. Coagulation pathway evaluation (for example by measurement of D-dimer levels) should probably be a component of studies with decitabine to treat hemoglobinopathies.

2. Neutropenia: Decitabine induced shifts in differentiation include favoring erythroidmegakaryocyte progenitor production over granulocyte-monocyte progenitor production by hematopoietic stem cells ($\underline{60}$, $\underline{61}$). Hence, even at low, non-cytotoxic concentrations, a downward shift in neutrophil counts is expected. Of note, the current standard of care for symptomatic SCD is DNA damaging, cytotoxic doses of HU. Consequently, in SCD subjects treated with HU,

hematologic toxicities are pancellular, with neutrophil recovery taking up to 2 weeks (AHFS Drug Information[®], 2000).

3. Lymphopenia: Decitabine induced shifts in hematopoietic differentiation may also reduce lymphocyte production.

3. Testicular toxicity: Pre-clinical studies suggest an effect on sperm-counts can occur even with the intended low, non-cytotoxic concentrations of decitabine. This toxicity appears reversible. Of note, the current standard of care for symptomatic SCD with HU also causes testicular toxicity (AHFS Drug Information[®], 2000).

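### Table 9 prints the platelet count for starting daily aspirin as above 500 per mcL; the multiplier is missing

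*Combined protocol and SAP*

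**What the plan says.** Table 9 in Section 3.3.5 lists the laboratory values that change DAC-THU treatment. Its thrombocytosis row has two tiers. The lower tier reads "If platelet count > 500/ mcL but < 1.2M/mcL, continue DAC-THU at current dose. Begin ASA 325mg PO daily". The upper tier, from 1.2M/mcL, holds DAC-THU until the count falls below that level and also starts aspirin 325 mg daily.

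The protocol's other per-mcL platelet thresholds are written at full scale:

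- Section 2.1.1.13 requires at least 100,000/mcL at entry.
- Section 2.1.2.14 excludes "Thrombocytosis defined as platelet count > 1,200,000/mcL".
- Section 4.1 says "Blood product support should be provided to maintain platelets > 20,000 cells/mcl".

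The background text uses a different unit. In the sickle cell study of Section 1.2.9 the platelet trigger appears as "neither a platelet count of > 1200 x 10⁹/L" and again as "> 1,200 x 10⁹/L for platelets". Section 13.1.9 describes an earlier decitabine study "despite concurrent platelet count increases to > 800x10⁹/L".

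**The concern.** A floor of 500/mcL does not work as a floor: every patient who meets the platelet entry criterion already exceeds it. The figure looks like a count in 10⁹/L, or in thousands, printed with a per-mcL unit and no multiplier.

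The row is an operative instruction to start a drug, and it is likely to be used. Rising platelet counts are an expected effect of decitabine (13.1.9). Blood counts are taken twice weekly in Course 1 and weekly afterwards (3.4.2). The exclusion criterion bars only counts above 1,200,000/mcL, so a patient may enrol with an elevated count. The protocol also names thrombocytopenia among the main toxicities it wants to avoid (3.1.3), so the start point for daily aspirin should be clear. As printed, two clinicians could treat the same moderately elevated count differently.

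**Working it through.** No sample-size or power figure is involved. The check puts every platelet threshold on one scale, cells per mcL.

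**Inputs**

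| Threshold | Source | As printed | Per mcL |
|---|---|---|---|
| Aspirin start, lower bound | Table 9 | 500/mcL | 500 |
| Hold DAC-THU | Table 9 | 1.2M/mcL | 1,200,000 |
| Entry minimum | 2.1.1.13 | 100,000/mcL | 100,000 |
| Exclusion | 2.1.2.14 | 1,200,000/mcL | 1,200,000 |
| Platelet support | 4.1 | 20,000/mcL | 20,000 |

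**Step 1. Is the printed floor plausible?**

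- Entry minimum ÷ printed floor: 100,000 / 500 = 200.
- Support level ÷ printed floor: 20,000 / 500 = 40.
- Upper bound of the same sentence ÷ printed floor: 1,200,000 / 500 = 2,400.

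The floor lies far below the level at which the protocol gives platelets, so it cannot mark the start of thrombocytosis.

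**Step 2. Which value fits?** Since 1 × 10⁹/L = 1,000/mcL, the background threshold of 1,200 × 10⁹/L equals 1,200,000/mcL. That matches both the printed 1.2M/mcL and the exclusion criterion. On the same scale 500 × 10⁹/L = 500,000/mcL, and 500,000 / 500 = 1,000. The resulting band of 500,000 to 1,200,000/mcL is coherent: its floor is 500,000 / 100,000 = 5 times the entry minimum, and its ceiling is 1,200,000 / 500,000 = 2.4 times its floor.

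**Step 3. Which patients are affected?** Three things confine the row to raised counts: its heading, the condition in Section 3.3.1.2 ("In the event of an adverse event at least possibly related to the investigational agent"), and the definition in Section 8.1.1, under which a laboratory value counts as an adverse event when it is abnormal. Normal and low counts are therefore not sent to aspirin. What remains are counts above the laboratory's upper limit of normal but below 500,000/mcL. For these the printed text starts aspirin and the inferred text does not.

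**Step 4. How wide is that zone?** The documents give no upper limit of normal for platelets. Assuming 350,000 to 450,000/mcL:

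- 500,000 − 450,000 = 50,000/mcL
- 500,000 − 350,000 = 150,000/mcL

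**Step 5. Is the floor stated elsewhere?** No other section of the supplied text restates the aspirin trigger. The only numerical definition of thrombocytosis is the exclusion limit of 1,200,000/mcL. That is the top of this band, so it cannot supply the bottom.

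**The case against.** The strongest reply is that the slip largely corrects itself. The row is headed thrombocytosis, the upper bound is right, and a clinician who sees that 500 is impossible will read 500,000. Treatment then diverges only if someone applies a figure that nobody believes. This has force and is a reason to rate the point minor. It does not remove it, because a drug-start threshold should not depend on the reader reconstructing it.

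Two further objections stand in part. The width of the ambiguous zone rests on an assumed upper limit of normal, so it illustrates the scale and is not a property of the plan. Limiting the row to elevated counts is also a reading of several sections together; the row itself does not say so.

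A character may have been lost when the PDF was read, and Table 9 is disordered in places. This cannot be fully excluded. However, all three M multipliers in the same cell survived and nothing marks a gap. Finally, this is a missing unit multiplier and not a failed calculation. That is fair as a description and leaves the error in place.

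**Conclusion.** The concern holds, as a minor correction to a safety instruction. The lower aspirin trigger in Table 9 is wrong as printed and is given correctly nowhere else in the supplied text. If 500 × 10⁹/L was meant, the printed figure lacks a factor of 1,000. That is a dropped multiplier and should not be described as a 1,000-fold treatment error.

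The practical effect is inconsistent aspirin use in patients whose count is raised but below the intended floor. DAC-THU continues at the current dose in this tier, and the hold level is printed correctly and agrees with the exclusion criterion. The response endpoint, sample size, alpha and power are untouched.

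The conclusion that the figure is wrong needs no outside assumption. The value of 500,000/mcL is inferred from the units used elsewhere, and the width of the ambiguous zone depends on the assumed upper limit of normal.

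**What to change.** The sponsor should confirm the intended floor, most likely 500,000/mcL. The lower tier should then be printed as > 500,000/mcL but < 1,200,000/mcL, and the next tier as 1,200,000/mcL or more, so that the row uses the same full-scale notation as Sections 2.1.1.13, 2.1.2.14 and 4.1. The cost is one table cell, with no change to the statistical design.

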3.3.6 Dose Delay of Pembrolizumab

No dose modification for pembrolizumab is allowed. Because of the potential for clinically meaningful pembrolizumab-related AEs requiring early recognition and prompt intervention, management algorithms have been developed for suspected AEs of selected categories. Dose delay criteria apply for all drug-related adverse events (regardless of whether or not the event is attributed to pembrolizumab). If AE is felt to be immune related and attributable to pembrolizumab, the patient can continue DAC-THU while pembrolizumab is held. Dose delay criteria apply for all drug-related AEs. Pembrolizumab must be delayed until treatment can resume.

3.3.6.1 Pembrolizumab Administration Should be Delayed for the Following:

Gastrointestinal irAEs				
Severity of Diarrhea/Colitis (NCI-CTCAE v5)	Initial Management	Follow-up Management		
Grade 1 Diarrhea: < 4 stools/day over Baseline Colitis: asymptomatic	Continue Pembrolizumab Symptomatic treatment (e.g. loperamide)	Close monitoring for worsening symptoms Educate subject to report worsening immediately If worsens: Treat as Grade 2, 3 or 4.		

Gastrointestinal irAEs				
Severity of Diarrhea/Colitis (NCI-CTCAE v5)	Initial Management	Follow-up Management		
Grade 2	Withhold Pembrolizumab	If improves to Grade ≤ 1 :		
Diarrhea: 4 to 6 stools per day over Baseline; IV fluids indicated < 24 hours; not interfering with ADL	Symptomatic treatment	Resume Pembrolizumab therapy		
Colitis: abdominal pain; blood in		If persists > 5-7 days or recurs:		
stool		Treat as Grade 3 or 4.		
Grade 3 to 4	Withhold Pembrolizumab for Grade 3.	If improves:		
Diarrhea (Grade 3): \geq 7 stools per day over Baseline; incontinence; IV fluids \geq 24 h; interfering with ADL	Permanently discontinue Pembrolizumab for Grade 4 or recurrent Grade 3.	Continue steroids until Grade ≤ 1 , then taper over at least 1 month; resume Pembrolizumab therapy		
Colitis (Grade 3): severe abdominal pain, medical intervention indicated,	1.0 to 2.0 mg/kg/day prednisone IV or equivalent	following steroids taper (for initial Grade 3).		
peritoneal signs Grade 4: life-threatening,	Add prophylactic antibiotics for opportunistic infections	If worsens, persists > 3 to 5 days, or		
perforation	Consider lower endoscopy	recurs after improvement:		
		Add infliximab 5mg/kg (if no contraindication). Note: infliximab should not be used in cases of perforation or sepsis.		

Dermatological irAEs					
Grade of Rash (NCI-CTCAE v5)	Initial Management	Follow-up Management			
Grade 1 to 2 Covering ≤ 30% body surface area	Continue Pembrolizumab Symptomatic therapy (for example, antihistamines, topical steroids)	If persists > 1 to 2 weeks or recurs: Withhold Pembrolizumab therapy Consider skin biopsy Consider 0.5-1.0 mg/kg/day prednisone or equivalent. Once improving, taper steroids over at least 1 month, consider prophylactic antibiotics for opportunistic infections, and resume Pembrolizumab therapy following steroids taper.			

Dermatological irAEs				
Grade of Rash (NCI-CTCAE v5)	Initial Management	Follow-up Management		
		If worsens: Treat as Grade 3 to 4.		
Grade 3 to 4 Grade 3: Covering > 30% body surface area; Grade 4: Life threatening consequences	 Withhold Pembrolizumab for Grade 3. Permanently discontinue for Grade 4 or recurrent Grade 3. Consider skin biopsy Dermatology consult 1.0 to 2.0 mg/kg/day prednisone or equivalent Add prophylactic antibiotics for opportunistic infections 	If improves to Grade ≤ 1: Taper steroids over at least 1 month; resume Pembrolizumab therapy following steroids taper (for initial Grade 3).		

Pulmonary irAEs				
Grade of Pneumonitis (NCI-CTCAE v5)	Initial Management	Follow-up Management		
Grade 1 Radiographic changes only	Consider withholding Pembrolizumab therapy	Re-assess at least every 3 weeks		
	Monitor for symptoms every 2 to 3 days	If worsens:		
	Consider Pulmonary and Infectious Disease consults	Treat as Grade 2 or Grade 3 to 4.		
Grade 2	Withhold Pembrolizumab therapy	Re-assess every 1 to 3 days		
Mild to moderate new symptoms	 Pulmonary and Infectious Disease consults Monitor symptoms daily; consider hospitalization 1.0 to 2.0 mg/kg/day prednisone or equivalent Add prophylactic antibiotics for opportunistic infections 	If improves: When symptoms return to Grade ≤ 1 , taper steroids over at least 1 month, and then resume Pembrolizumab therapy following steroids taper		
	Consider bronchoscopy, lung biopsy	If not improving after 2 weeks or worsening:		

Pulmonary irAEs		
Grade of Pneumonitis (NCI-CTCAE v5)	Initial Management	Follow-up Management
		Treat as Grade 3 to 4.
Grade 3 to 4 Grade 3: Severe new symptoms; New/worsening hypoxia;	Permanently discontinue Pembrolizumab therapy. Hospitalize.	If improves to Grade ≤ 1 : Taper steroids over at least 1 month
Grade 4: Life-threatening	 Pulmonary and Infectious Disease consults. 1.0 to 2.0 mg/kg/day prednisone or equivalent Add prophylactic antibiotics for opportunistic infections Consider bronchoscopy, lung biopsy 	If not improving after 48 hours or worsening: Add additional immunosuppression (for example, infliximab, cyclophosphamide, IV immunoglobulin, or mycophenolate mofetil)

Hepatic irAEs		
Grade of Liver Test Elevation (NCI-CTCAE v5)	Initial Management	Follow-up Management
Grade 1 Grade 1 AST or ALT > ULN to 3.0	Continue Pembrolizumab therapy	Continue liver function monitoring
x ULN and/or Total bilirubin > ULN to 1.5 x ULN		If worsens: Treat as Grade 2 or 3 to 4.
Grade 2	Withhold Pembrolizumab therapy	If returns to Grade ≤ 1 :
AST or ALT > 3.0 to ≤ 5 x ULN and/or total bilirubin > 1.5 to ≤ 3 x ULN	Increase frequency of monitoring to every 3 days.	Resume routine monitoring; resume Pembrolizumab therapy.
		If elevation persists > 5 to 7 days or worsens:
		Treat as Grade 3 to 4.
Grade 3 to 4 AST or ALT > 5 x ULN and/or total	Permanently discontinue Pembrolizumab therapy	If returns to Grade ≤ 1 : Taper steroids over at least 1 month
bilirubin > 3 x ULN	Increase frequency of monitoring to every 1 to 2 days	
	1.0 to 2.0 mg/kg/day prednisone or equivalent	If does not improve in > 3 to 5 days, worsens or rebounds:

Hepatic irAEs		
Grade of Liver Test Elevation (NCI-CTCAE v5)	Initial Management	Follow-up Management
	Add prophylactic antibiotics for opportunistic infections	Add mycophenolate mofetil 1 gram (g) twice daily
	Consult gastroenterologist/ hepatologist Consider obtaining MRI/CT scan of liver and liver biopsy if clinically warranted	If no response within an additional 3 to 5 days, consider other immunosuppressants per local guidelines.

Renal irAEs		
Grade of Creatinine Increased (NCI-CTCAE v5)	Initial Management	Follow-up Management
Grade 1 Creatinine increased > ULN to 1.5 x ULN	Continue Pembrolizumab therapy	Continue renal function monitoring If worsens: Treat as Grade 2 to 3 or 4.
Grade 2 to 3 Creatinine increased > 1.5 and ≤ 6 x ULN	Withhold Pembrolizumab therapy Increase frequency of monitoring to every 3 days and consider Nephrology consult 1.0 to 2.0 mg/kg/day prednisone or equivalent. Add prophylactic antibiotics for opportunistic infections Consider renal biopsy	If returns to Grade ≤ 1: Follow Nephrology recommendations if consult obtained; alternatively, taper steroids over at least 1 month, and resume Pembrolizumab therapy following steroids taper. If worsens: Treat as Grade 4.
Grade 4 Creatinine increased > 6 x ULN	Permanently discontinue Pembrolizumab therapy Monitor creatinine daily 1.0 to 2.0 mg/kg/day prednisone or equivalent. Add prophylactic antibiotics for opportunistic infections Consider renal biopsy Nephrology consult	If returns to Grade ≤ 1: Follow Nephrology recommendations; alternatively, taper steroids over at least 1 month.

Cardiac irAEs		
Myocarditis	Initial Management	Follow-up Management
New onset of cardiac signs or symptoms and / or new laboratory cardiac biomarker elevations (e.g., troponin, CK-MB, BNP) or cardiac imaging abnormalities suggestive of myocarditis.	Withhold Pembrolizumab therapy. Hospitalize. In the presence of life threatening cardiac decompensation, consider transfer to a facility experienced in advanced heart failure and arrhythmia management. Cardiology consult to establish etiology and rule-out immune-mediated myocarditis. Guideline based supportive treatment as per cardiology consult. * Consider myocardial biopsy if recommended per cardiology consult.	If symptoms improve and immune-mediated etiology is ruled out, re-start Pembrolizumab therapy. If symptoms do not improve/worsen, viral myocarditis is excluded, and immune-mediated etiology is suspected or confirmed following cardiology consult, manage as immune-mediated myocarditis.
Immune-mediated myocarditis	Permanently discontinue Pembrolizumab. Guideline based supportive treatment as appropriate as per cardiology consult. * 1.0 to 2.0 mg/kg/day prednisone or equivalent. Add prophylactic antibiotics for opportunistic infections.	Once improving, taper steroids over at least 1 month. If no improvement or worsening, consider additional immunosuppressants (e.g. azathioprine, cyclosporine A).

ESC guidelines website: https://www.escardio.org/Guidelines/Clinical-Practice-Guidelines

AHA guidelines website:

http://professional.heart.org/professional/GuidelinesStatements/searchresults.jsp?q=&y=&t=1001

Endocrine irAEs		
Endocrine Disorder	Initial Management	Follow-up Management
Grade 1 or Grade 2 endocrinopathies (hypothyroidism, hyperthyroidism, adrenal insufficiency, type I diabetes mellitus)	Continue Pembrolizumab therapy Endocrinology consult if needed Start thyroid hormone replacement therapy (for hypothyroidism), anti-thyroid treatment (for hyperthyroidism), corticosteroids (for adrenal insufficiency) or insulin (for Type I diabetes mellitus) as appropriate.	Continue hormone replacement/suppression and monitoring of endocrine function a appropriate.

Endocrine irAEs		
Endocrine Disorder	Initial Management	Follow-up Management
	Rule-out secondary endocrinopathies (i.e., hypopituitarism / hypophysitis)	
Grade 3 or Grade 4 endocrinopathies (hypothyroidism, hyperthyroidism, adrenal insufficiency, type I diabetes mellitus)	Withhold Pembrolizumab therapy Consider hospitalization Endocrinology consult	Resume Pembrolizumab once symptoms and/or laboratory tests improve to Grade ≤ 1 (with or without hormone replacement/suppression).
	Start thyroid hormone replacement therapy (for hypothyroidism), anti-thyroid treatment (for hyperthyroidism), corticosteroids (for adrenal insufficiency) or insulin (for type I diabetes mellitus) as appropriate.	Continue hormone replacement/suppression and monitoring of endocrine function as appropriate.
	Rule-out secondary endocrinopathies (i.e. hypopituitarism / hypophysitis)	
Hypopituitarism/Hypophysitis (secondary endocrinopathies)	If secondary thyroid and/or adrenal insufficiency is confirmed (i.e. subnormal serum FT4 with inappropriately low TSH and/or low serum cortisol with inappropriately low ACTH):	Resume Pembrolizumab once symptoms and hormone tests improve to Grade ≤ 1 (with or without hormone replacement).
	• Refer to endocrinologist for dynamic testing as indicated and measurement of other hormones (FSH, LH, GH/IGF-1, PRL, testosterone in men, estrogens in women)	In addition, for hypophysitis with abnormal MRI, resume Pembrolizumab only once shrinkage of the pituitary gland on MRI/CT scan is documented.
	• Hormone replacement/suppressive therapy as appropriate	Continue hormone replacement/suppression therapy as appropriate.
	• Perform pituitary MRI and visual field examination as indicated	
	If hypophysitis confirmed:	
	• Continue Pembrolizumab if mild symptoms with normal MRI. Repeat the MRI in 1 month	

	Endocrine irAEs		
Endocrine Disorder	Initial Management	Follow-up Management	
	 Withhold Pembrolizumab if moderate, severe or life- threatening symptoms of hypophysitis and/or abnormal MRI. Consider hospitalization. Initiate corticosteroids (1 to 2 mg/kg/day prednisone or equivalent) followed by corticosteroids taper during at least 1 month. Add prophylactic antibiotics for opportunistic infections. 		

Other irAEs (not described above)		
Grade of other irAEs (NCI-CTCAE v5)	Initial Management	Follow-up Management
Grade 2 or Grade 3 clinical signs or symptoms suggestive of a potential irAE	Withhold Pembrolizumab therapy pending clinical investigation	If irAE is ruled out, manage as appropriate according to the diagnosis and consider re-starting Pembrolizumab therapy If irAE is confirmed, treat as Grade 2
		or 3 irAE.
Grade 2 irAE or first occurrence of Grade 3 irAE	Withhold Pembrolizumab therapy	If improves to Grade ≤ 1 :
	1.0 to 2.0 mg/kg/day prednisone or equivalent	Taper steroids over at least 1 month and resume Pembrolizumab therapy following steroids taper.
	Add prophylactic antibiotics for opportunistic infections	
	Specialty consult as appropriate	
Recurrence of same Grade 3 irAEs	Permanently discontinue Pembrolizumab therapy	If improves to Grade ≤ 1 :
	to 2.0 mg/kg/day	Taper steroids over at least 1 month.
	prednisone or equivalent	
	Add prophylactic antibiotics for opportunistic infections	
	Specialty consult as appropriate	
Grade 4	Permanently discontinue Pembrolizumab therapy	If improves to Grade ≤ 1 : Taper steroids over at least 1 month
	to 2.0 mg/kg/day	

Other irAEs (not described above)		
Grade of other irAEs (NCI-CTCAE v5)	Initial Management	Follow-up Management
	prednisone or equivalent and/or other immunosuppressant as needed Add prophylactic antibiotics for	
	opportunistic infections	
	Specialty consult.	
Requirement for 10 mg per day or greater prednisone or	Permanently discontinue Pembrolizumab therapy	
equivalent for more than 12 weeks for reasons other than	Specialty consult	
hormonal replacement for adrenal insufficiency		
Persistent Grade 2 or 3 irAE lasting 12 weeks or longer		

ADL=activities of daily living, ALT=alanine aminotransferase, AST=aspartate aminotransferase, irAE=immune-related adverse event, IV=intravenous, LLN=lower limit of normal, MRI=magnetic resonance imaging, NCI-CTCAE=National Cancer Institute-Common Terminology Criteria for Adverse Event, NSAIDs=nonsteroidal anti-inflammatory drugs, T4=thyroxine, TSH=thyroid-stimulating hormone, ULN=upper limit of normal, IVIG=intravenous immunoglobulins, CPK=creatine phosphokinase.

Note: Subjects who require delay of pembrolizumab should be re-evaluated closely as clinically indicated and resume pembrolizumab dosing when re-treatment criteria are met.

